3. STUDY DESIGN

This is a Phase 3, randomized, double-blind study to evaluate the antiviral efficacy, safety and tolerability of tenofovir DF versus placebo in pediatric subjects with chronic HBV infection. One hundred (100) tenofovir DF-naïve subjects with HBV DNA $\geq 10^5$ copies/mL and ALT $\geq 1.5 \times$ ULN will be randomized in a 2:1 ratio to treatment arm A or B:

- Treatment A (n = 67): tenofovir DF PO once daily for 48 weeks
- Treatment B (n = 33): matching placebo PO once daily for 48 weeks

After 48 weeks of blinded randomized treatment, each subject will switch to open-label tenofovir DF treatment for additional 144 weeks (see study schema at end of Section 3). Subjects under Protocol Amendment 3 who are beyond Week 48 of blinded randomized treatment will switch to open-label tenofovir DF at the Week 72 visit and will continue on open-label treatment until Week 192.

Randomization will be stratified by age (2 to < 6 and 6 to < 12) and geographical location of study site (North America/Europe and Asia).

Randomization cannot occur until after the Baseline (pre-treatment) DEXA scan has been performed.

Subjects who experience Grade 4 ALT while on blinded study medication will be evaluated weekly with serum chemistry and liver function test monitoring. In the event that any subject has sustained Grade 4 ALT for ≥ 16 weeks (i.e., failure to resolve ALT to grade ≤ 3 or baseline), the serial HBV DNA values on study will be provided to the investigator, and the subject can be offered open-label tenofovir DF, after discussion with the Gilead Medical Monitor. Such events should be recorded as an adverse event leading to blinded study drug discontinuation.

All subjects will take a daily multivitamin with no additional mineral components that contain a minimum of 400 IU of vitamin D or higher per country specific regulations.

The primary efficacy and safety analysis will be conducted at the end of double-blind treatment, after the last randomized subject reaches Week 48. Subsequently, efficacy and safety analyses of all subjects continuing on open-label tenofovir DF will be performed after the last randomized subject reaches Weeks 144 and 192.

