4.3. Exclusion Criteria

Subjects who meet *any* of the following exclusion criteria are not to be enrolled in this study.

- Pregnant or lactating subjects.
- Sexually-active males or females of childbearing potential who are not willing to use a highly effective method of contraception during the study. (see Section 7.7.2 for further details).
- Decompensated liver disease defined as PT $> 1.2 \times$ ULN, platelets $< 150,000/\text{mm}^3$, serum albumin < 3.5 g/dL, or prior history of clinical hepatic decompensation (e.g., ascites, jaundice, encephalopathy, variceal hemorrhage).
- Receipt of interferon (pegylated or not) therapy within 6 months of the Screening Visit
- Receipt of anti-HBV nucleoside/nucleotide therapy within 16 weeks of the Screening Visit
- α -fetoprotein > 50 ng/mL
- Evidence of hepatocellular carcinoma (HCC)
- Co-infection with HIV, acute HAV, HCV, or HDV
- Chronic liver disease of non-HBV etiology (e.g., hemochromatosis, alpha-1 antitrypsin deficiency, cholangitis)
- History of significant renal disease (e.g., nephrotic syndrome, renal dysgenesis, polycystic kidney disease, congenital nephrosis, acute tubular necrosis, other renal disease)
- History of significant bone disease (e.g., osteomalacia, chronic osteomyelitis, osteogenesis imperfecta, osteochondroses, multiple bone fractures)
- Significant cardiovascular, pulmonary or neurological disease
- Evidence of a gastrointestinal malabsorption syndrome that may interfere with absorption of orally administered medications

- History of solid organ or bone marrow transplantation
- Ongoing therapy with any of the following:
 - Nephrotoxic agents
 - Parenteral aminoglycoside antibiotics (e.g., gentamicin, tobramycin, amikacin)
 - Cidofovir
 - Cisplatin
 - Foscarnet
 - IV amphotericin B
 - IV pentamidine
 - Oral or IV ganciclovir
 - Cyclosporine
 - Tacrolimus
 - IV vancomycin
- Chronic daily non-steroidal anti-inflammatory drug therapy
 - Competitors of renal excretion (e.g., probenecid)
 - Systemic chemotherapeutic agents
 - Systemic corticosteroids (pulmonary administration via MDI/nebulizer and oral steroids administered for less than 5 days are permitted)
 - Interleukin-2 (IL-2) and other immunomodulating agents
 - Investigational agents (except with the expressed approval of the Sponsor)
 - Administration of any of the above medications must be discontinued at least 45 days prior to the Baseline Visit and for the duration of the study period.

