5.4.2. During the Study

Use of the following medications is prohibited while subjects are on study drug:

- Antiviral agents with anti-HBV activity, including lamivudine, emtricitabine, entecavir, adefovir, telbivudine, clevudine, or others
- Interferon-alfa and pegylated interferon-alfa
- Nephrotoxic agents such as aminoglycoside antibiotics, cidofovir, cisplatin, foscarnet, IV amphotericin B, IV pentamidine, ganciclovir, cyclosporine, tacrolimus, chronic daily non-steroidal anti-inflammatory drugs, or other agents with significant nephrotoxic potential

- Hepatotoxic agents such as anabolic steroids, isoniazid, itraconazole, ketoconazole, lovastatin, rifabutin, rifampin, simvastatin, and other agents with significant hepatotoxic potential
- Competitors of renal excretion, such as probenecid
- Systemic chemotherapeutic agents
- Interleukin-2 [IL-2]) and other immunomodulating agents
- Systemic corticosteroids (pulmonary administration via MDI/nebulizer and oral steroids administered for less than 5 days are permitted)
- Investigational agents, except with written approval of the Sponsor

Should subjects need to start treatment with any excluded concomitant medication, the Sponsor must be consulted prior to initiation of the new medication. In instances where an excluded medication is initiated prior to discussion with the Sponsor, the Investigator must notify the Sponsor as soon as s/he is aware of the use of the excluded medication.

All concomitant medications, including vitamin supplements, herbal remedies and hormonal contraception, must be recorded in the appropriate section of the Case Report Forms.

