- If ALT remains $> 2 \times$ baseline and $> 10 \times$ ULN and the bilirubin or PT values are confirmed at $> 2.5 \times$ ULN or $> 1.5 \times$ ULN, respectively, the investigator should consider discontinuing study medication and initiating alternative HBV therapy (see below). However, prior to initiating alternative therapy, medical management of the subject should be discussed with the Gilead Medical Monitor. (Note: Once a subject has started alternative therapy, s/he must be discontinued from the study.)

Elevated Liver Enzymes, Elevated Bilirubin and PT/INR ($>$ Grade 2), Symptomatic Elevated Lactate ($> 2 \times$ ULN) or Asymptomatic Elevated Lactate ($> 4 \times$ ULN)

If ALT/AST values are elevated (i.e., $> 2 \times$ baseline and $> 10 \times$ ULN) and bilirubin or PT values are confirmed at $> 2.5 \times$ ULN or $> 1.5 \times$ ULN, respectively, or lactate levels are increased (symptomatic and $> 2 \times$ ULN or asymptomatic and $> 4 \times$ ULN) the investigator should consider discontinuing study medication and initiating alternative HBV treatment. The subject must be monitored weekly for as long as enzyme levels and bilirubin and PT/INR remain elevated or above baseline values. Refer to [Appendix 6](#) for specific guidelines for the management of symptomatic and asymptomatic hyperlactatemia.

- If the ALT/AST levels return to the baseline level and/or Grade 2 or lower during the first 8 weeks of monitoring, study medication may be resumed.
- If the ALT/AST levels, bilirubin, PT/INR or lactate levels remain elevated up through Week 8 or deteriorate at any point, the investigator should consult with the Gilead Medical Monitor.

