3.1.4. Per Protocol Analysis Set

The Per Protocol (PP) Analysis Set will include all subjects who (1) were randomized into the study, (2) had received at least 1 dose of study drug, and (3) had not been excluded based on criteria below. Subjects will be analyzed according to the treatment they actually received during the double-blind phase. The PP analysis set is the secondary analysis set for the efficacy analysis.

Subjects meeting any of the following criteria will be excluded from the Week 48 PP Analysis Set:

- Subjects who do not have on-treatment HBV DNA in the Week 48 analysis window, except for subjects who discontinue study drug due to lack of efficacy. (Note: lack of efficacy is defined as having the check-box for “Efficacy Failure” marked as the reason for premature study drug discontinuation on the study drug completion eCRF page). The details are summarized in [Table 3-1](#).

Table 3-1. Subjects Excluded from Per Protocol Analysis Set Due to Premature Discontinuation and/or Missing HBV DNA Assessment in Week 48 Analysis Window

Discontinuation from Study Drug Prior to or on the Upper Bound of Week 48 Analysis Window		HBV DNA Data on Randomized Treatment Available in Week 48 Analysis Window	
		Yes	No
Yes	Due to Lack of Efficacy	+	+
	Due to Other Reasons	+	-
No		+	-

+ = Inclusion of Subjects in Per Protocol Analysis Set; - = Exclusion of Subjects in Per Protocol Analysis Set

- Subjects who meet the exclusion criterion for receiving ongoing therapy with any of the prohibited medications listed in the clinical study protocol (Section 4.3).
- Subjects with less than 80% adherence rate for study drug up to the Week 48 visit.

A listing of subjects in the FAS, but were excluded from the PP Analysis Set, will be provided with the reason for exclusion specified.

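### The Per Protocol medication exclusion in SAP 3.1.4 points only to protocol Section 4.3, so it does not remove a subject who takes an anti-HBV antiviral banned on study by Section 5.4.2

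*SAP*

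**What the plan says.** SAP 3.1.4 defines the PP set as randomized and treated subjects less three groups: those without an on-treatment HBV DNA value in the Week 48 window (with an exception for Efficacy Failure, set out in Table 3-1), those below 80% adherence to study drug, and "Subjects who meet the exclusion criterion for receiving ongoing therapy with any of the prohibited medications listed in the clinical study protocol (Section 4.3"). SAP 6.1.4 repeats the primary analysis in this set.

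The list cited from protocol Section 4.3 covers nephrotoxic agents, chronic daily NSAIDs, competitors of renal excretion, chemotherapy, systemic corticosteroids, IL-2 and other immunomodulators, and investigational agents. It is not limited to entry: these drugs "must be discontinued at least 45 days prior to the Baseline Visit and for the duration of the study period". Section 4.3 deals with anti-HBV nucleos(t)ides in a separate bullet, which is a washout before entry: "Receipt of anti-HBV nucleoside/nucleotide therapy within 16 weeks of the Screening Visit".

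The on-study ban is in protocol Section 5.4.2, which names "Antiviral agents with anti-HBV activity, including lamivudine, emtricitabine, entecavir, adefovir, telbivudine, clevudine, or others" and, as a separate item, interferon-alfa and pegylated interferon-alfa. If a banned drug is needed, "the Sponsor must be consulted prior to initiation of the new medication". The section also foresees that this may not happen: "In instances where an excluded medication is initiated prior to discussion with the Sponsor, the Investigator must notify the Sponsor" afterwards. It does not itself require study drug to stop.

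**The concern.** A PP analysis is meant to show the result in subjects who followed the protocol on matters that bear on the endpoint. Here the endpoint is HBV DNA below 69 IU/mL. The rule as written excludes a chronic NSAID user but keeps a subject who took entecavir or lamivudine alongside blinded drug, although only the latter acts directly on HBV DNA.

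The bias can go either way. Added antiviral therapy in a placebo subject pulls the comparison towards no difference; in a TDF subject it flatters TDF. The FAS analysis counts such a subject by the observed HBV DNA value, so PP is the planned analysis from which one would expect the subject to be removed. SAP 3.1 fixes set membership before the blind is broken, so the rule has to be right by then.

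**Working it through.** **Does any other rule catch the subject?** Take a subject who has recorded use of a Section 5.4.2 antiviral, continues blinded drug, is at least 80% adherent and has an HBV DNA value in the Week 48 window.

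| Rule | What it looks at | Removes the subject or sets failure? |
|---|---|---|
| SAP 3.1.4, medication criterion | Section 4.3 list | No: no anti-HBV nucleos(t)ide is listed |
| SAP Table 3-1 | Discontinuation; Week 48 HBV DNA available | No |
| SAP 3.1.4 and 4.3.2, adherence | Blinded drug only | No |
| SAP 3.8.2, on-treatment status | Study-drug dates | No |
| SAP 6.1.3, Missing = Failure | Missing values | No: the value is present |
| SAP 4.4, important deviations | Reported if classed as important | No: summarized and listed only |
| SAP 7.8, concomitant medications | All recorded use | No: summarized and listed only |
| Protocol 7.6.6.1 | Conduct after an ALT flare | No: not a PP criterion |

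The gap is clear for nucleos(t)ides. For interferon it is arguable, because the immunomodulator entry in Section 4.3 may cover it, although Section 5.4.2 lists the two separately.

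**The plan's own figure.** SAP 1.3 claims at least 85% power for 67 v 33 subjects at 21% v 1% with a two-sided Fisher test. Full enumeration gives 88.3%, which agrees. This point does not dispute the figure.

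**Size of the effect.** Inputs:
- 90 subjects randomized (SAP 1.3). The split by arm is not given; 2:1 is assumed, so 60 TDF and 30 placebo.
- TDF response 80% (SAP 1.3): 0.80 × 60 = 48 responders.
- The planned test is the CMH test with four strata (two age groups by two regions). Stratum sizes are not given, so three TDF/placebo splits were assumed: 15,15,15,15/8,8,7,7; 6,10,10,34/3,5,5,17; 4,8,16,32/2,4,8,16. The 48 TDF responders were spread proportionally, and every placement of y placebo responders was enumerated.

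One contaminated responder shifts the placebo rate by 1/30 = 3.3 points or the TDF rate by 1/60 = 1.7 points.

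CMH statistic (1 df, no continuity correction): [Σ(x − n1·m/N)]² / Σ[n1·n2·m·(N − m)/(N²(N − 1))]. In each stratum x is TDF responders, n1 and n2 are the arm sizes, m is total responders and N = n1 + n2.

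| Placebo responders y of 30 | CMH p, range over splits and placements | Unstratified Fisher p |
|---|---|---|
| 1 | 1.46e-11 to 1.73e-11 | 5.8e-13 |
| 17 | 0.011 to 0.024 | 0.026 |
| 18 | 0.028 to 0.051 | 0.075 |

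**The case against.** **The event is improbable, and this stands.** Protocol Section 5.1 withholds HBV DNA results during blinding except for an ALT flare or Grade 4 ALT lasting 16 weeks, so there is normally no virologic cue to add an antiviral. In those two situations the protocol foresees an end to blinded drug. For an ALT flare, "Once a subject has started alternative therapy, s/he must be discontinued from the study". For sustained Grade 4 ALT the subject may be offered open-label tenofovir DF, and "Such events should be recorded as an adverse event leading to blinded study drug discontinuation". A subject who stops blinded drug and then switches can contribute an on-treatment value reflecting only about 3 days of the new drug, because SAP 3.8.2 closes that period 3 days after the last dose. What remains is add-on use outside these routes. These are conduct rules, however, and do not take a subject who breached them out of PP.

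**Recorded use would be visible.** SAP 7.8 lists it, and SAP 4.4 reports it by arm if it is classed as an important deviation. This also stands, but visibility is not exclusion. Undisclosed use would escape both the present rule and the amended one.

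**PP is a supporting set.** The SAP added it (SAP 6.4), and it lies outside the gatekeeping procedure. That limits the weight of the point without making the cross-reference correct.

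**Stronger readings that a reader might infer:**
- *The PP result could flip on a few subjects.* At the original 21% TDF rate (13/60) with no other placebo responders, two contaminated placebo subjects would move Fisher p from 0.004 to 0.081. But SAP 1.3 now works with 80% and cites 86.5% at Week 48 in adolescents, and nothing suggests that such use is frequent.
- *The primary analysis is affected.* The PP wording does not enter the FAS analysis.
- *The Section 4.3 list applies only at entry.* It runs for the study period. The defect is the missing drug class.
- *The adherence convention should change too.* SAP 4.3.2 takes a missing returned amount as zero, which can only raise calculated adherence, but dropping the period has its own error. With 79% adherence over 280 days and a fully taken 56-day period of unknown return, true adherence is (0.79 × 280 + 56)/336 = 82.5%; dropping the period scores 79% and wrongly excludes the subject. Neither convention is clearly better, so no change is proposed.

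**Conclusion.** The point holds as a minor error in a set definition. SAP 3.1.4 cites the wrong list for the drugs that matter most to the endpoint, and no other rule removes a subject with recorded on-study use of an anti-HBV nucleos(t)ide who otherwise qualifies for PP. The consequence is small: 3.3 points per placebo responder or 1.7 points per TDF responder. Roughly 18 of 30 placebo responders would be needed before the planned test approaches 0.05. These figures rest on the assumed 60:30 split, 80% TDF response and the three assumed stratum patterns. The documents give no frequency for the event.

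**What to change.** Before the blind is broken, keep the Section 4.3 reference in SAP 3.1.4 and add: *or who took any anti-HBV antiviral, interferon-alfa or pegylated interferon-alfa prohibited in protocol Section 5.4.2 between the first blinded dose and the selected Week 48 HBV DNA sample or, if there is no such sample, the last blinded dose.* The last part gives the window an end for Efficacy Failure subjects, whom Table 3-1 keeps without a Week 48 sample. State that the clause does not override Table 3-1 for Efficacy Failure subjects whose other drug began only after the last blinded dose. Naming interferon settles whether Section 4.3 covers it. The clause need not extend to the other Section 5.4.2 drugs.

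The cost is one clause. Section 5.4.2 already requires all concomitant medications on the case report form, so no new data and no extra analysis are needed. The downside is that a few more subjects may leave the PP set.

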3.1.5. Serologically Evaluable Full Analysis Set

3.1.5.1. Serologically Evaluable Full Analysis Set for HBeAg loss/seroconversion

The Serologically Evaluable Full Analysis Set for HBeAg loss/seroconversion will include all subjects who were randomized and had received at least 1 dose of study drug, and with HBeAg positive and HBeAb negative or missing at baseline. Subjects will be analyzed according to the treatment to which they were randomized.

3.1.5.2. Serologically Evaluable Full Analysis Set for HBsAg loss/seroconversion

The Serologically Evaluable Full Analysis Set for HBsAg loss/seroconversion will include all subjects who were randomized and had received at least 1 dose of study drug, and with HBsAg positive, defined as HBsAg level ≥ 0.07 IU/mL, and HBsAb negative or missing at baseline. Subjects will be analyzed according to the treatment to which they were randomized.

3.1.6. DXA Analysis Set

3.1.6.1. Spine DXA Analysis Set

The Spine DXA Analysis Set will include all subjects who were randomized and had received at least 1 dose of study drug, and had nonmissing baseline spine bone mineral density (BMD) values. Subjects will be analyzed according to the treatment they actually received during the double-blind phase.

3.1.6.2. Whole Body DXA Analysis Set

The Whole Body DXA Analysis Set will include all subjects who were randomized and had received at least 1 dose of study drug, and had nonmissing baseline whole body BMD values. Subjects will be analyzed according to the treatment they actually received during the double-blind phase.

3.2. Subject Grouping

For analyses based on the Full Analysis Set including the Serologically Evaluable Full Analysis Sets, subjects will be grouped according to the treatment to which they were randomized. For analyses based on the Per Protocol Analysis Set, Safety Analysis Set, Spine DXA Analysis Set, Whole Body DXA Analysis Set, subjects will be grouped according to the actual treatment received during the double-blind phase. The actual treatment received will differ from the randomized treatment only when their actual treatment differs from randomized treatment for the entire double-blind treatment duration.

3.3. Strata and Covariates

Randomization was stratified by age (2 to <6 and 6 to <12 years at the time of enrollment) and geographical location of study site (North America/Europe, and Asia). For all stratified analyses, age at baseline (<6 and ≥ 6 years) and geographical location of study site (North America/Europe, and Asia) will be used. If the number of subjects in a particular stratum is too small, this stratum may be combined with other strata for analysis. If there are discrepancies in stratification factor values between the IWRS and the clinical database at screening or baseline, the values recorded in the clinical database at baseline (or screening, if baseline is missing) will be used for stratified analyses.

3.4. Examination of Subject Subgroups

The primary efficacy endpoint of the proportion of subjects with HBV DNA < 69 IU/mL (400 copies/mL) at Week 48 will be examined using the following subgroups:

- Baseline ALT: (a) $\leq 2 \times \text{ULN}$ and (b) $> 2 \times \text{ULN}$
- By American Association for the Study of Liver Diseases (AASLD) normal range (ULN is 30 U/L for pediatric subjects {[Terrault 2016](#)})
- By central laboratory normal range (ULN is 34 U/L for females between 2-15 years old or males between 1-9 years old and 43 U/L for males between 10-15 years old)
- Sex: (a) male and (b) female
- Age at baseline: < 6 vs ≥ 6 years old
- Region: (a) Asia and (b) North America/Europe
- Baseline HBV DNA: (a) $< 8 \log_{10}$ IU/mL, (b) $\geq 8 \log_{10}$ IU/mL

3.5. Multiplicity Adjustments

A sequential gatekeeping procedure will be employed. The key secondary efficacy endpoint of the proportion of subjects with HBeAg seroconversion at Week 48 will be tested at a 0.05 level, only if the primary endpoint of the proportion of subjects with HBV DNA < 69 IU/mL (400 copies/mL) at Week 48 is statistically significant at a 0.05 level.

3.6. Missing Data and Outliers

3.6.1. Missing Data

A missing datum for a given study analysis window may be due to any of the following reasons:

- A visit occurring in the window but data were not collected or were unusable
- A visit not occurring in the window
- A subject permanently discontinuing from the study before reaching the window

For the primary endpoint and the secondary efficacy endpoints involving proportions, missing data will be handled using a Missing = Failure (M = F) approach. Sensitivity analyses will also be performed using a Missing = Excluded (M = E) approach.

For the remaining endpoints, values for missing data will not be imputed, unless specified otherwise.

3.6.2. Outliers

Outliers will be identified during the data management and data analysis process, but no sensitivity analyses will be conducted. All data will be included in the data analysis.

3.7. Data Handling Conventions and Transformations

In general, age (in years) on the date of the first dose of study drug will be used for analyses and presentation in listings. If an enrolled subject was not dosed with any study drug, the randomization date will be used instead of the first dosing date of study drug. For screen failures, the date the informed consent was signed will be used for age calculation. If only the birth year is collected on the eCRF, “01 July” will be used for the unknown birth day and month for the purpose of age calculation. If only birth year and month are collected, “01” will be used for the unknown birth day.

Non-PK data that are continuous in nature but are less than the lower limit of quantitation (LOQ) or above the upper LOQ will be imputed as follows:

A value that is 1 unit less than the LOQ will be used to calculate descriptive statistics if the datum is reported in the form of “< x” (where x is considered the LOQ). For example, if the values are reported as < 50 and < 5.0, values of 49 and 4.9, respectively, will be used to calculate summary statistics. An exception to this rule is any value reported as < 1 or < 0.1, etc. For values reported as < 1 or < 0.1, a value of 0.9 or 0.09, respectively, will be used to calculate summary statistics.

A value that is 1 unit above the LOQ will be used to calculate descriptive statistics if the datum is reported in the form of “> x” (where x is considered the LOQ). Values with decimal points will follow the same logic as above.

The LOQ will be used to calculate descriptive statistics if the datum is reported in the form of “≤ x” or “≥ x” (where x is considered the LOQ).

For HBV DNA, if the value in IU/mL (HBV DNA PCR TaqMan assay) is above the upper limit of quantification, the corresponding diluted value (HBV DNA PCR TaqDil assay), if available, will be used.

If methods based on the assumption that the data are normally distributed are not adequate, analyses may be performed on transformed data or nonparametric analysis methods may be used, as appropriate. Specifically, logarithm (base 10) will be used to transform HBV DNA and quantitative HBsAg data.

